APPENDIX II-A

COHORT 1 INFANT SCHEDULE OF EVALUATIONS
(CLOSED)

	Birth	1-5 hours after birth	8-14 hours after birth	18-24 hours after birth	30-36 hours after birth	Week 1-2	Week 20
CLINICAL EVALUATIONS							
History						X ²	X ²
Physical exam	X ¹					X ³	X ³
LABORATORY EVALUATIONS							
Hematology ^{4,6}			0.5 mL			0.5mL	
Chemistries ^{5,6}			1mL		1mL	1mL	
VIROLOGY							
Genotyping ⁷					Dried Blood Spot		
PHARMACOKINETICS*							
Washout ⁸		1mL	1mL	1mL	1mL		
TOTAL BLOOD	0mL	1mL	2.5mL	1mL	2 mL	1.5mL	0mL

*See section 3.0 and 4.3 for criteria for infants eligible for pharmacokinetic blood sampling.

1. Physical examination includes infant Apgar score, birth weight and length, gestational age, gender, sex, and ethnicity.
2. History includes all non-protocol laboratory tests, HIV test results, antiretroviral agents (for PMTCT), concomitant medications, and any intercurrent illnesses since the last visit.
3. Complete physical exam includes temperature, heart rate, respiratory rate, weight, length, and head circumference.
4. Hematology includes CBC (complete blood count) with differential and platelet count.
5. Chemistries include AST, ALT, creatinine and total and direct bilirubin.
6. Infants not eligible for pharmacokinetic sampling will have hematology and chemistries obtained at 8-14 hours after birth and at 1-2 weeks of age, with additional chemistries at 30-36 hours after birth.
7. Genotyping (optional) for UGT1A1 polymorphisms will be done using dried blood spot on filter paper. Only infants who have pharmacokinetic sampling will have genotyping done. (Option: Can collect at week 1-2 if unable to obtain immediately after birth).
8. Only infants eligible for pharmacokinetic blood sampling (See Section 3.0 and 4.3). Collect 1mL of blood for each sample

Priority of blood draw should be as follows: 1) Chemistries; 2) Hematology; 3) Pharmacokinetics; 4) Genotyping

APPENDIX II-B
COHORT 2 INFANT SCHEDULE OF EVALUATIONS

	Birth/Entry	1-6 hours after birth ¹¹	12-24 hours after birth ¹¹	36-48 hours after birth	72-84 hours after birth	108-132 hours after birth	Week 1-2 (7-14 days after birth)	Week 6 (35-49 days after birth)
CLINICAL EVALUATIONS								
History				X ²			X ²	X ²
Physical exam	X ¹						X ³	X ³
LABORATORY EVALUATIONS (if not obtained for standard of care)								
Hematology ^{4,6}				0.5mL ⁴			0.5mL	
Chemistries ^{5,6}					1mL ⁵		1mL	
Bilirubin ^{6,7}				1mL ⁷				
PHARMACOGENETICS¹⁰								
Genotyping ⁸					0.125mL			
PHARMACOKINETICS^{*10}								
Washout ⁹		0.25 mL	0.25 mL	0.25 mL	0.25mL	0.25mL	0.25mL	
TOTAL BLOOD	0mL	0.25mL	0.25mL	1.75mL	1.375mL	0.25mL	1.75mL	0mL

*See section 3.0 and 4.6 for criteria for infants eligible for pharmacokinetic (PK) blood sampling.

1. Physical examination includes infant Apgar score, birth weight and length, head circumference, gestational age, gender, sex, and ethnicity.
2. History includes all non-protocol laboratory tests, HIV test results, antiretroviral agents for PMTCT, concomitant medications, signs and symptoms, diagnoses, and any intercurrent illnesses since the last visit, including any treatment to reduce bilirubin.
3. Complete physical exam includes temperature, heart rate, respiratory rate, weight, length, and head circumference.
4. Hematology to include CBC with differential and platelet count: If hematology testing was done as part of clinical care within 48 hours, report values obtained for clinical care and do not obtain additional study sample.
5. Chemistries include AST, ALT, creatinine and total and direct bilirubin: If chemistry testing was done as part of clinical care within 24 hours, report values obtained for clinical care and do not obtain additional study sample.
6. Both PK eligible and ineligible infants will have laboratory evaluations collected unless obtained as part of clinical care (see Footnotes 4, 5, and 7). If infant enrolls after birth, hematology, chemistries, and bilirubin should be obtained with first PK blood draw for those infants eligible for PK.
7. Bilirubin includes total and direct: If bilirubin testing was done as part of clinical care within 24 hours, report values obtained for clinical care and do not obtain additional study sample.
8. Genotyping (optional) for UGT1A1 polymorphisms will be done using dried blood spot on filter paper. Only infants who have PK sampling will have genotyping.
9. Only infants eligible for PK blood sampling (See Section 3.0 and 4.3). Collect 0.25mL of blood for each sample. Infants enrolled after delivery up to 48 hours may not have the initial PK samples obtained but will start as soon as possible. (Note: Infants enrolled close to the 48-hour time point should have the first PK blood sample collected within 4 hours of enrollment (i.e., within 52 hours after birth).
10. See the Laboratory Processing Chart (LPC) on the P1097 Protocol Specific Webpage on the IMPAACT Website (<http://www.impaactgroup.org>) for collection, processing and shipping instructions.
11. Skip visit if enrolled after scheduled time of visit.

Priority of blood draws should be: chemistries, hematology, pharmacokinetics, genotyping.

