- **Infant not receiving disallowed medications described in Section 4.8. If these medications are required for the infant's care, the infant will be ineligible for further PK (pharmacokinetic) sampling. Data will be obtained up to the time of the introduction of the disallowed medication, but such infant will not be considered one of the evaluable 15 infants.**
- **Infant \leq 48 hours of age.**

Blood samples for raltegravir assay will be collected at 1-6, 12-24, 36-48, 72-84, and 108-132 hours after birth, and on day 7-14. Infants may enroll up to 48 hours of age, and any pharmacokinetic samples scheduled for collection prior to the time of enrollment will be skipped and not replaced. Infants enrolling close to the 48-hour time point should have the first pharmacokinetic blood sample collected within 4 hours of enrollment (i.e., within 52 hours after birth) so that a minimum of three blood samples can be obtained for pharmacokinetic evaluation.

With regard to infant blood samples for safety/toxicity laboratory testing: In the event that the study-required study safety/lab samples have not been collected prior to enrollment, (e.g., due to infant enrolled after delivery), these must be collected as soon as possible after enrollment. To meet the primary objectives of the study, only those infants who have at least 3 pharmacokinetic blood samples collected from the first 5 time points will be considered to be evaluable.

Optional genotyping for polymorphisms of UGT1A1 **were performed on Cohort 1 infants and** will be performed **on Cohort 2** infants who undergo pharmacokinetic sampling. **The goal of the genotypic analysis** is to determine if certain polymorphisms, particularly those with the UGT1A1*28/*28 genotype have slower RAL elimination than those with the UGT1A1*1/*1 genotype. Because UGT1A1 activity is reduced in neonates, polymorphisms associated with reduced activity are likely to have a larger impact on the metabolism of raltegravir, especially those who are low birth weight.

No study-specific drugs will be given to women or infants during this study. Women will be receiving raltegravir for clinical indications outside of the study. Infants will receive standard of care antiretroviral therapy for prevention of mother-to-child transmission (PMTCT) as prescribed by their primary care physicians.

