8.4 Sample Size and Accrual

The target accrual for Cohort 1 was 15 evaluable infants which was projected to require enrolling up to 25 M-I pairs and approximately 12 months to fully accrue. Cohort 1 is fully accrued with 19 evaluable infants (22 M-I pairs).

Cohort 2 will enroll M-I pairs until a total of 15 evaluable infants are accrued which is projected to require enrolling up to 20 M-I pairs. The projected accrual period is 12 months. Evaluable infants will be those who have at least 3 PK blood samples collected following the PK schedule in Section 9.3.

This is a pilot study aimed at gathering information needed for the design of a follow-up study that will evaluate a neonatal raltegravir dosing regimen. The sample size of 15 evaluable infants reflects the judgment of the team pharmacologists with respect to the amount of washout pharmacokinetic data needed to design the later follow-up dosing study. It is based on practical considerations and experience with other antiretroviral drugs such as nevirapine and tenofovir in pregnant women and their neonates [47-50].

All infants enrolled to the study, including those not evaluable for the washout pharmacokinetic analysis, will be included in the safety analyses. The study is not powered for analysis of the safety data so that no hypothesis testing will be done but descriptive summary statistics will be calculated. Given the relatively small study sample, the precision of the estimates will be relatively low and the confidence interval (CI) estimates will be relatively wide. Table 2 shows the precision with which rates of serious adverse events can be estimated, given the sample size of 15, 20 or 25 infants.

Table 2. Point and 90% confidence interval estimates of proportion of infants meeting the toxicity endpoint^a

Number of infants	Proportion of infants meeting toxicity endpoint	90% CI of proportion of infants meeting the toxicity endpoint
15	0.00	(0.00, 0.22)
	0.20	(0.04, 0.48)
	0.40	(0.16, 0.68)
	0.60	(0.32, 0.84)
	0.80	(0.52, 0.96)
	1.00	(0.78, 1.00)
20	0.00	(0.00, 0.17)
	0.20	(0.06, 0.44)
	0.40	(0.19, 0.64)
	0.60	(0.36, 0.81)
	0.80	(0.56, 0.94)
	1.00	(0.83, 1.00)
25	0.00	(0.00, 0.14)
	0.20	(0.07, 0.41)
	0.40	(0.21, 0.61)
	0.60	(0.39, 0.79)
	0.80	(0.59, 0.93)
	1.00	(0.86, 1.00)

^a Clopper-Pearson exact confidence interval estimates using SAS Version 9.2.

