3.3.2 Secondary Study Objective Analysis

Neonatal RAL elimination ($T_{1/2}$) for infants with versus without polymorphisms on UGT1A1 will be summarized using summary statistics and the comparison of median for these groups will be done using the Wilcoxon Sum Rank Test ($\alpha=0.05$). Analysis will be limited to infants with non-missing RAL elimination and UGT1A1 polymorphism data. There may be limited statistical power for this analysis if there is small sample size.

4 Report Contents

Detailed descriptions of the content of each of the following sections are given in the AIP.

- 1) Accrual (M-I pairs, Infants, PK evaluable infants) and eligibility criteria violations**
- 2) Baseline characteristics**
- 3) Study status**
- 4) Data completeness**
- 5) Safety data**
- 6) Neonatal RAL elimination and UGT1A1 genotype**

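### Cohort 2 UGT1A1 genotyping has one scheduled draw (72-84 h) and no stated fallback, so a missed spot can drop a PK-evaluable infant from the only secondary analysis

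*Protocol*

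**What the plan says.** The Cohort 2 infant schedule (Protocol Appendix II-B) has a single genotyping entry, 0.125 mL. Footnote 8 makes it an optional dried blood spot and restricts it by sampling status: "Only infants who have PK sampling will have genotyping". That sentence settles who is genotyped. When it happens is given only by the table row. The blood-draw instruction under the table reads "Priority of blood draws should be: chemistries, hematology, pharmacokinetics, genotyping".

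Footnote 7 of the Cohort 1 schedule (Appendix II-A) has essentially the same content plus one provision that Cohort 2 lacks: "Option: Can collect at week 1-2 if unable to obtain immediately after birth". The priority order was the same in Cohort 1: "Priority of blood draw should be as follows: 1) Chemistries; 2) Hematology; 3) Pharmacokinetics; 4) Genotyping".

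Evaluability does not depend on the 72-84 h sample. Protocol Section 3.0 says "only those infants who have at least 3 pharmacokinetic blood samples collected from the first 5 time points will be considered to be evaluable", and Section 8.4 says "Cohort 2 will enroll M-I pairs until a total of 15 evaluable infants are accrued". The relation between elimination and genotype is the only secondary objective (Protocol 2.2). For that analysis SAP 3.3.2 states "Analysis will be limited to infants with non-missing RAL elimination and UGT1A1 polymorphism data" and plans a rank-sum test at the 0.05 level. SAP 1.3 and 3.1 keep the two cohorts apart, so Cohort 1 genotypes cannot fill a gap in Cohort 2.

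**The concern.** Germline genotype is the same on day 3 as on day 10, so nothing scientific ties the spot to one visit. The half-life is the expensive measurement, built from several timed samples in an infant of 2500 g or less. The genotype needs 0.125 mL at any draw. A schedule with one slot and no stated alternative allows the half-life to be obtained and then go unused in the genotype comparison because the spot was missed.

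There are two routes. The infant may miss the 72-84 h visit but supply three of the other four early samples. Or the visit takes place but the draw is short: chemistries and the PK sample rank above the spot, so the PK sample can be secured and the spot not. With a target of 15 evaluable infants, and possibly very few in the smaller genotype group, one or two such losses could matter.

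**Working it through.** **1. Is there really only one slot?** The column totals in Appendix II-B settle where the 0.125 mL belongs.

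- 36-48 h: 0.5 (hematology) + 1 (bilirubin) + 0.25 (PK) = 1.75 mL, as stated.
- 72-84 h: 1 (chemistries) + 0.125 (genotyping) + 0.25 (PK) = 1.375 mL, as stated.
- Week 1-2: 0.5 + 1 + 0.25 = 1.75 mL, as stated.
- 1-6 h, 12-24 h and 108-132 h: 0.25 mL each (PK only), as stated.

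Only the 72-84 h total contains the spot, so the single slot is not a text-extraction fault.

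**2. Can an infant be PK evaluable without that visit?** Sets of at least 3 of the first 5 time points: C(5,3) + C(5,4) + C(5,5) = 10 + 5 + 1 = 16. Sets that omit 72-84 h: C(4,3) + C(4,4) = 4 + 1 = 5. By first available sample:

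| First available sample | Evaluable patterns | Of these, omit 72-84 h |
|---|---|---|
| 1-6 h | 16 | 5 |
| 12-24 h | 5 | 1 |
| 36-48 h | 1 | 0 |

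These are counts of patterns, not probabilities. They cover the missed-visit route only. The short-draw route is open to any infant, including late enrollees.

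**3. How many genotypes might be lost?** The documents give no rate. Assume each of 15 evaluable infants independently lacks a spot with probability m. Expected genotyped = 15(1 - m); chance of losing at least one = 1 - (1 - m)^15.

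| Assumed m | Expected genotyped | Chance of at least one lost |
|---|---|---|
| 5% | 14.25 | 54% |
| 10% | 13.5 | 79% |
| 20% | 12.0 | 96% |
| 30% | 10.5 | above 99% |

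**4. What could a loss do to the test?** The smallest two-sided exact rank-sum p for k infants in one group out of n, without ties, is 2/C(n,k). The SAP does not state sidedness; two-sided is assumed.

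- 15 infants, two *28/*28: 2/105 = 0.019.
- 14 infants, one *28/*28: 2/14 = 0.143. Rejection at 0.05 is impossible. One-sided, 1/14 = 0.071, it is still impossible.
- 15 infants, one *28/*28: 2/15 = 0.133, already impossible with nothing missing.
- Broader grouping, for example 4 against 10: 2/C(14,4) = 2/1001 = 0.002. One lost genotype does not close off the test.

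**5. How often would at least two *28/*28 infants be genotyped?** Binomial, with assumed frequencies that are not in the documents.

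| Assumed *28/*28 frequency | 15 genotyped | 13 genotyped | 12 genotyped |
|---|---|---|---|
| 5% | 17% | 14% | 12% |
| 10% | 45% | 38% | 34% |
| 15% | 68% | 60% | 56% |
| 20% | 83% | 77% | 73% |

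Losing three genotypes of 15 costs about 5 to 12 percentage points; losing two costs about 4 to 8.

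**The case against.** A reader might infer that a missed spot is lost for good. The documents do not support that. They are silent on later collection; they do not forbid it. PK-eligible infants still have draws at 108-132 h and at day 7-14, and footnote 10 sends sites to a Laboratory Processing Chart that is not part of the protocol or SAP and may address the matter.

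A reader might also infer that last priority is a new weakness. It is not, since Cohort 1 used the same order. The slot itself falls after the last possible enrollment (48 h) and the latest first PK draw (52 h), so no infant misses it through late enrollment. The competing 1 mL of chemistries is not drawn when clinical care supplied results within 24 hours (footnote 5).

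Nor does stopping PK sampling early by itself remove the genotype. An infant with earlier PK samples meets footnote 8's wording, and footnote 6 keeps laboratory draws for PK-ineligible infants. Whether an infant who stopped because of a disallowed medication can count as evaluable is a separate matter: Protocol Section 3.0 excludes that infant outright, Sections 4.3 and 4.7 only if fewer than three samples were collected, and these need reconciling.

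Finally, the step from 0.019 to 0.143 is a chosen case. Exactly two *28/*28 infants among 15 has probability 0.27, 0.29 or 0.23 at frequencies of 10%, 15% or 20%. Losing exactly one of them at m = 20% has probability 2 x 0.2 x 0.8 = 0.32, which gives about 7% to 9% overall. At a 10% frequency the chance of fewer than two is already 55% with complete genotyping, so scarcity outweighs scheduling. The case also depends on the grouping: SAP 1.5 names *28/*28, while SAP 3.3.2 compares infants by presence of any UGT1A1 polymorphism. The SAP already concedes limited power.

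All of this stands and limits the size of the point. It does not supply the missing fallback, which the sponsor considered worth writing down for Cohort 1.

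**Conclusion.** The point holds as a minor gap. Cohort 2 genotyping has one scheduled time, and the fallback given to Cohort 1 was not carried over. As written, a PK-evaluable infant can end up without a scheduled opportunity for genotyping, and the complete-case rule in SAP 3.3.2 then excludes that infant from the only secondary analysis.

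The documents do not allow the loss to be sized. Under the assumed miss rates of 5% to 30%, the expected number genotyped falls from 15 to between 14.25 and 10.5. Whether that matters to the test depends on the unknown *28/*28 frequency and on which of the two SAP groupings is used. It would be too strong to say that the plan makes the secondary comparison unable to reach significance: that follows only if the smaller group falls to a single infant, which can happen with no missing spots at all. No primary PK or safety analysis is affected.

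**What to change.** Add one sentence to Appendix II-B footnote 8: if the spot is not obtained at 72-84 h, it may be collected at any other study blood draw through week 1-2, for any infant who had at least one PK sample. The last clause makes explicit what footnote 8 arguably already allows for infants who later stop PK sampling.

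The cost is small. The assay and volume are already planned, and 0.125 mL moves from one draw to another. If week 1-2 is used, that draw rises from 1.75 to 1.875 mL. The infant's scheduled total stays at 0.25 + 0.25 + 1.75 + 1.375 + 0.25 + 1.75 = 5.625 mL. If the Laboratory Processing Chart already permits later collection, the sentence only brings the schedule into line with it.

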1.1 Purpose of the Statistical Analysis Plan

This Primary Statistical Analysis Plan (SAP) describes the primary and secondary outcomes measures of IMPAACT P1097 that will be included in the primary manuscript addressing the primary and secondary objectives of the study. This document outlines the general statistical approaches that will be used in the analysis for administrative and safety data. It also describes the results for the primary and secondary outcome measures that will be posted on ClinicalTrials.gov. Detailed outlines of tables, figures, and coding descriptions that will be included in the primary statistical analysis report are included in the Analysis Implementation Plan (AIP). SAP and AIP have been developed to facilitate discussion of the statistical analysis components amongst the study team; and to provide agreement between the study team and statisticians regarding the statistical analyses to be performed and presented in the primary statistical analysis report.

The SAP includes the components for the data analysis of P1097 Versions 1.0 and 2.0 for Cohorts 1 and 2, respectively. The pharmacology data will be analyzed separately by the protocol pharmacologist.

The primary statistical analysis report will be used for submission of results to ClinicalTrials.gov. Results for primary outcomes are required to be submitted within one year of the primary completion date (PCD), which is the date the last participant is examined for the purposes of data collection for the primary outcome measure. For this study, the PCD is based on 6 weeks of infant follow-up.

1.2 Key Updates to the SAP

- 1. Primary SAP (this document) and Analysis Implementation Plan (AIP) were created based on specifications in SAP Version 2.0. Primary SAP covers outcome measures, general analytic approaches, and overview of the analysis report content. AIP includes more specific coding details, data sources, validation requirements, and table/figure specifications. There were no changes to the planned analyses for the primary and secondary study objectives.**
- 2. The following were added:**
 - a. description of submission to ClinicalTrials.gov**
 - b. wide visit windows for checking availability of safety data**
 - c. sections on report contents, writing team roster, and timeline for Final Analysis Report and manuscript preparation.**
- 3. Updated proposed analyses for Cohort 2 so that prematurity and growth restriction, which are considered highly linked to LBW, will be considered baseline.**

1.3 Protocol Overview

P1097 is a multi-center clinical trial to determine the washout pharmacokinetics (PK) and safety of in utero/intrapartum exposure to raltegravir (RAL) in infants born to pregnant women with

HIV1 infection who received at least one dose of RAL 400mg within 2 to 24 hours prior to delivery.

The IMPAACT P1097 Protocol includes two cohorts of Mother-Infant (M-I) pairs:

- Cohort 1 (Fully accrued under Protocol Version 1.0): pregnant women with HIV1 infection receiving RAL 400mg twice daily for at least two weeks prior to delivery and continuing to receive ARVs during labor, and their infants.
- Cohort 2 (Opened to accrual under Protocol Version 2.0): pregnant women with HIV1 infection who received at least one dose of RAL 400mg within 2 to 24 hours prior to delivery and their low birth weight (LBW) infants.

Cohort 1 was fully accrued and closed to follow-up under Version 1.0. The protocol was amended to open a cohort for LBW infants (≤ 2500 grams at birth) in Protocol Version 2.0. The primary and secondary objectives of the protocol are the same for both cohorts. Data analysis will be done separately for the two cohorts and no across cohort analysis will be done.

Cohort 1 total accrual was 22 M-I pairs and there were 19 evaluable infants for the RAL washout PK analysis. The M-I pairs were enrolled prior to delivery. Infant blood samples for RAL assay were collected at 1-5, 8-14, 18-24 and 30-36 hours after birth. Maternal blood sample and cord blood sample were also collected during delivery. Team pharmacologists decided if infants were PK evaluable or not. PK unevaluable infants will still remain in the study and will be followed for safety.

Cohort 2 will enroll up to 20 M-I pairs to achieve 15 evaluable LBW infants for the washout PK of RAL. The M-I pairs will be enrolled prior to delivery or within 48 hours after birth. Infant blood samples for RAL assay will be collected at 1-6, 12-24, 36-48, 72-84 and 108-132 hours after birth, and on day 7-14. When possible, maternal blood sample and cord blood sample will be collected during delivery. The washout PK analysis will be based on infants from whom at least 3 neonate blood specimens were collected from the first 5 time points (PK analyses will be done by the protocol pharmacologist). PK unevaluable infants will still remain in the study and will be followed for safety.

Women will be followed until discharge from the labor/delivery unit. Cohort 1 infants were followed for 20 weeks. Cohort 2 infants will be followed for 6 weeks.

